7.7.2 Secondary Efficacy Analysis

The secondary efficacy analysis is to evaluate the proportion of subjects achieving FXI inhibition $\geq 50\%$, $\geq 80\%$, and $\geq 90\%$ at trough after the first and second dose (Day 31 and Day 61) at 3 dose levels of MAA868. The analyses described for the primary endpoint will be repeated for the secondary efficacy variables as follows:

- Cohort 1 (MAA868 120 mg monthly or placebo): at Day 31 and 61.
- Cohort 2 (MAA868 180 mg monthly or placebo): at Day 31 and 61
- Cohort 3 (MAA868 TBD mg monthly or placebo): at Day 31 and 61

No comparisons to the placebo or statistical tests will be conducted for the primary efficacy endpoint.

7.7.3 Sensitivity Analysis

There are no planned sensitivity analyses.

7.7.4 Subgroup Analysis

There are no planned subgroup analyses.

7.7.5 Exploratory Analysis

There are no exploratory efficacy endpoints.

7.8 Safety

All safety analysis will be presented by actual treatment group and overall using the safety set.

7.8.1 Extent of Exposure and Compliance

Study drug exposure will not be summarized for this study. Dose compliance will be summarized by treatment group and overall for the MAA868 arms only.

7.8.2 Adverse Events (AE)

All AEs recorded on the eCRF will be coded using the MedDRA dictionary version 22.0. Treatment-emergent Adverse Events (TEAEs) will be of primary interest and are defined as:

- AEs with a start date on or after the date of first dose of study drug and up to the EoS visit
- AEs with start date prior to the date of first dose of study drug whose severity worsens on or after the date of first dose of study drug

TEAEs will be summarized by system organ class (SOC) and preferred term (PT) by treatment group and overall. Subject counts and percentages and event counts will be presented for the following TEAE summaries:

- All TEAEs
- Serious TEAEs
- All TEAEs by severity
- All TEAEs by relationship to study drug
- TEAEs potentially related to study drug
- TEAEs potentially related to study drug by severity
- TEAEs leading to discontinuation of study drug
- TEAEs leading to withdrawal from study

A subject will only be counted once per SOC and once per PT. If a subject reports more than one AE with the same PT, the AE with the maximum severity will be presented. AE severity grades are mild, moderate, or severe. An AEs relationship to study drug is assessed as related, possibly related, or not related.

If the start date/time of an AE is incomplete or missing, the AE will be assumed to be a TEAE, unless the incomplete start date/time or the end date/time indicates an AE started prior to the start of the infusion. AEs with missing causality are assumed

Statistical Analysis Plan

Sponsor Name: Anthos

Sponsor Protocol ID: ANT-004

Covance Study ID: 000000189471

to be related. If the severity of an AE is missing, the AE will be counted under the maximum severity possible.

Listings will be presented by subject for TEAEs, AESIs, serious AEs (SAEs), AEs leading to discontinuation of study drug, and AEs resulting in death.

No statistical comparisons of AEs between treatment groups will be performed.

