3. INVESTIGATION PLAN

3.1. Overall Study Design and Plan Description

This is a phase 2a, randomized, subject- and investigator-blinded, placebo-controlled, multiple ascending dose-ranging study to assess the PK/PD, safety, tolerability, and immunogenicity of MAA868 in patients with AF or flutter.

Patients will be enrolled in at least 2 and up to 3 cohorts of approximately 16 patients each for a total of up to 48 subjects (Figure 1A). Patients in cohort 1 will be randomized 3:1 to receive a 120 mg dose of MAA868 or placebo, respectively on Day 1 with two subsequent monthly injections. After approximately 10 of the patients in cohort 1 have been randomized, a safety review of emerging safety and PK data from cohort 1 will take place. Cohort 2 may be initiated after it is confirmed by the Sponsor’s Medical Monitor and the Covance Lead Project Physician that the cohort 1 dose was safe and well tolerated after at least half of the patients in cohort 1 have been randomized. Likewise, after approximately 10 of the patients in cohort 2 have received their second dose and have been followed for at least an additional 14 days, interim safety, tolerability, and other analyses will be evaluated by the Sponsor. Based on emerging data, the Sponsor may elect to:

[figure not shown]
- Enroll cohort 3 to evaluate a higher, lower, or a previously studied dose of MAA868
- Terminate the study

The study is comprised of 3 periods:

- (1) Screening period of up to 28 days
- (2) Treatment period with MAA868 administered s.c. monthly (or matching placebo) (randomized 3:1) for 90 days
- (3) Follow-up period up to end of study (Day 170).

Following the screening period of up to 28 days, all patients that meet the study eligibility criteria (Section 4.1 and Section 4.2) will have baseline efficacy and safety assessments performed on Day 1 and then randomized to active or placebo (Figure 1B).

Figure 1: Overall study design

The first dose of study drug will be administered at the study center on Day 1. The second and third doses of study drug will also be administered at the study center to patients on the Day 31 visit and Day 61 visit, respectively.

During the treatment period, patients will return to the study center on Day 11, Day 31, Day 41, Day 61, Day 71, and Day 91 for safety assessments such as vital signs, AE assessments, laboratory tests, PK, PD, thrombogenesis biomarkers, and other study assessments according to the assessment schedule shown in [Table 9](#).

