6.1 Time points and Visit Windows

Day 1 is defined as the day subjects receive the first dose of study drug. Relative days after Day 1 are calculated as (assessment date – Day 1 date) + 1. Relative days prior to Day 1 are calculated as (assessment date – Day 1 date). The day prior to Day 1 is Day -1.

Baseline is defined as the most recent result obtained prior to first administration of study medication. This occurs at visit 2 (day 1 pre-dose). If the assessment is not performed at visit 2, the value from visit 1 (screening) will be used. If this value is not present, there will be no baseline value.

Trough FXI levels will only be used if they are considered "on treatment". A measurement is considered "on treatment" if it is collected within 30 (± 5) days after the last administration of MAA868.

CONFIDENTIAL

Page 13 of 28

Statistical Analysis Plan

Sponsor Name: Anthos
Sponsor Protocol ID: ANT-004

Covance Study ID: 000000189471

All data will be analyzed using nominal study visits as defined in the schedule of assessments and eCRF. Unscheduled visits will be listed but not tabulated. No visit windows will be applied for summary and analysis.

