6.2.2 Missing Data

The occurrence of missing data related to the primary endpoint is considered a protocol deviation. Endpoint analyses will use observed data only – no imputation methods are planned.

Imputations of missing and partial dates are given below and to be used only for the following: assessment of treatment emergence status of an AE; determination of study day/time of onset and duration of an AE; definitions of prior and concomitant medications.

Missing or Partial Start Dates

- Missing time – the minimum possible onset time will be calculated and presented in '≥DD:HH:MM' format
- Missing day – impute the 1st of the month unless month is same as month of first dose of study drug then impute first dose date.
- Missing day and month – impute 1st January unless year is the same as first dose date then impute first dose date.
- Completely missing – impute first dose date unless the end date suggests it could have started prior to this in which case impute the 1st of January of the same year as the end date.

Missing or Partial End Dates

- Missing time – the maximum possible duration will be calculated and presented in '≤DD:HH:MM' format
- Missing day – impute the last day of the month unless month is same as month of first dose of study drug then impute last dose date.
- Missing day and month – impute 31st December unless year is the same as first dose date then impute last dose date.

CONFIDENTIAL

Page 14 of 28

Statistical Analysis Plan

Sponsor Name: Anthos
Sponsor Protocol ID: ANT-004

Covance Study ID: 000000189471

- Completely Missing – need to look at whether the AE/medication is still ongoing before imputing a date and when it started in relation to study drug. If the ongoing flag is missing, then assume that AE is still present / medication is still being taken (i.e., do not impute a date). If the AE/medication has stopped and start date is prior to first dose date then impute the 1st dose date, if it started on or after first dose date then impute a date that is after the last dose date.

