7.8.8 Bleeding Events

Subject counts and percentages and event counts for the number of treatment-emergent adjudicated bleeding events will be summarized by treatment group and overall. The definition of treatment-emergent can be found in [section 7.7.2](#). The following summaries will be presented:

- Major bleeding events
- Clinically relevant non-major bleeding events
- Nuisance (not clinically relevant) bleeding events
- No bleeding event

If a subject has more than one bleeding event in each above category, the subject will be counted only once in the tabulation. All adjudicated bleeding events will be listed.

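### SAP 7.8.2 counts an AE starting on Day 1 before the first injection as treatment-emergent, while its own rule for incomplete starts can exclude one shown to precede dosing

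*SAP*

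**What the plan says.** SAP 7.8.2 gives two routes to treatment emergence. The first is for new events: "AEs with a start date on or after the date of first dose of study drug and up to the EoS visit". The second is for worsening: "AEs with start date prior to the date of first dose of study drug whose severity worsens on or after the date of first dose". Both compare dates; neither mentions time of day.

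The same section adds a rule for AEs whose start is incomplete or missing. They are assumed treatment-emergent "unless the incomplete start date/time or the end date/time indicates an AE started prior to the start of the infusion". This rule does use time, and it refers to an infusion although the drug is given subcutaneously.

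SAP 6.1 fixes the calendar: "Day 1 is defined as the day subjects receive the first dose of study drug". On baseline it says "This occurs at visit 2 (day 1 pre-dose"), with screening as the fallback. Protocol 3.1 gives the same order of events: patients "will have baseline efficacy and safety assessments performed on Day 1 and then randomized to active or placebo". In Protocol Table 9 the Day 1 column is headed as pre-dose, and only the injection-site inspection is marked post-dose.

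SAP 6.2.2 provides for AE onset times: "Missing time – the minimum possible onset time will be calculated".

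For bleeding, SAP 7.8.8 states: "Subject counts and percentages and event counts for the number of treatment-emergent adjudicated bleeding events will be summarized by treatment group and overall". Sections 7.8.8 and 7.8.10 both refer to 7.7.2 for the meaning of treatment-emergent. Section 7.7.2 is the secondary efficacy analysis and contains no such definition. The protocol's bleeding analysis (Section 8.6) opens its window at the first dose itself.

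**The concern.** An event that began before the first injection cannot be an effect of the drug. Read literally, SAP 7.8.2 still places it in the TEAE tables if it carries the Day 1 date, and the finding behind it may also be that subject's baseline value. The SAP already recognises that timing relative to dosing matters, because its rule for incomplete records uses it. A fully documented pre-dose event is thus treated less accurately than a poorly documented one.

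The tables are descriptive and the groups small (12 on MAA868 and 4 on placebo per cohort), so a single subject is visible. What is at stake is the accuracy of the safety tables, not a hypothesis test.

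**Working it through.** The plan states no figure for this rule, so there is none to reproduce. The check is a reading of the rules, followed by simple arithmetic on group size.

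**Step 1: can a pre-dose Day 1 event be an AE?** Protocol 7.6.1 collects AEs from consent, and Protocol 7.4 ends medical history at consent. A new event between consent and the injection is therefore an AE. Abnormal tests are AEs only if they cause symptoms, are clinically significant or need therapy (Protocol 7.6.1). Protocol 7.12 supplies a concrete path: it foresees clinically significant ECG findings at baseline, to be discussed with the sponsor before dosing, and requires clinically significant abnormalities to go in the AE CRF.

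**Step 2: how does SAP 7.8.2 classify it?**

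| AE record | The two bullets (dates) | Incomplete-start rule (date/time) |
|---|---|---|
| Starts Day 1, time recorded, before injection | Treatment-emergent | Does not apply |
| Starts Day 1, no start time, end time before injection | Treatment-emergent | Not treatment-emergent |
| Starts Day 1, no start time, nothing else known | Treatment-emergent | Treatment-emergent |
| Starts before Day 1, worsens on Day 1 before injection | Treatment-emergent | Does not apply |

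Row 2 is a direct conflict. Rows 1 and 2 together show a complete pre-dose record counted and a less complete one excluded. Row 4 shows that the second bullet shares the problem.

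**Step 3: effect of one subject.** Group sizes are from Protocol 5.3 (12:4 per cohort).

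- MAA868 dose group: 1/12 = 8.3 points.
- Placebo pooled over two cohorts: 1/(2×4) = 1/8 = 12.5 points.
- Placebo pooled over three cohorts: 1/(3×4) = 1/12 = 8.3 points.

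These are maxima. A subject counts once per system organ class and preferred term, so one who has another qualifying event adds nothing to that row.

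**Step 4: how likely is at least one?** The documents give no rate. Assume a proportion q of 2–5%. The chance is 1 − (1 − q)^N and the expected number is N×q. Cohort 3 is optional, so N is 32 or 48.

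| N | q | Chance of at least one | Expected subjects |
|---|---|---|---|
| 32 | 2% | 1 − 0.98^32 = 48% | 0.64 |
| 32 | 5% | 1 − 0.95^32 = 81% | 1.6 |
| 48 | 2% | 1 − 0.98^48 = 62% | 0.96 |
| 48 | 5% | 1 − 0.95^48 = 91% | 2.4 |

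**Step 5: direction.** Pre-dose events are equally likely in every arm. For illustration, assume true rates of 20% and 10% with q = 5%, independent of later events. The observed rates are 1 − 0.80×0.95 = 24.0% and 1 − 0.90×0.95 = 14.5%. The difference falls from 10.0 to 9.5 points and the ratio from 2.0 to 1.66. The effect is dilution, with no arm favoured.

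**The case against.** The strongest defence is that a date rule may be the only workable one. Protocol 7.6.1 requires AE start and end dates, not times, and the eCRF is not among the documents. The time format in SAP 6.2.2 and the word 'infusion' may be template text. A date rule is also conservative, since no genuine post-dose Day 1 event is lost. This stands as a limit on the remedy: without recorded times, only findings traceable to the pre-dose visit can be reclassified. It does not remove the conflict within 7.8.2.

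A reader might infer more than the documents support:

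- *That treatment emergence rests on calendar date throughout.* It does not; the incomplete-start rule uses date and time.
- *That every abnormal Day 1 value becomes a TEAE.* Only findings that meet the AE criteria do. Investigators may record as medical history an abnormality they judge to precede consent, eligibility is rechecked on Day 1, and baseline stool samples may be collected up to 72 hours from Day 1.
- *That bleeding counts would be inflated.* Known active bleeding at baseline is an exclusion. A small venepuncture bruise would at most be a nuisance bleed, because the hematoma examples for clinically relevant non-major bleeding start at 25 cm², or 100 cm² if provoked (Protocol Appendix 5). Sections 7.8.8 and 7.8.10 inherit nothing from 7.8.2 until their references are corrected.
- *That thromboembolic counts would be affected.* The documents suggest no plausible pre-dose event of this kind in a subject who is then dosed.

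It is also fair that a pre-dose event would normally be judged unrelated, and that TEAEs are tabulated by relationship and listed, so a careful reader could find it.

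**Conclusion.** The point holds as an inconsistency in SAP 7.8.2 with a small consequence. By the two bullets, a qualifying AE that starts or worsens on Day 1 before the injection is treatment-emergent. By the incomplete-start rule, one shown to precede dosing is not. The date rule, if carried into the bleeding table, would also depart from the protocol window, which opens at the first dose and not at its calendar date.

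The misclassification is non-differential in expectation, and no statistical comparison of AEs is planned, so it does not bias the trial towards either arm. Its importance is that a single subject shows in groups of 8 to 12. The probabilities rest entirely on the assumed 2–5%; the sizes per subject rest only on the planned allocation. This is a minor wording correction.

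**What to change.** In SAP 7.8.2:

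1. Define treatment emergence in both bullets as onset, or worsening, at or after the date and time of the first injection where a time is recorded.
2. Keep Day 1 events without a time as treatment-emergent unless the record shows they were found at the pre-dose Visit 2 assessments.
3. Count pre-dose events, including those dated Day 1, as treatment-emergent only if they worsen after dosing.
4. Replace 'infusion' with 'first injection'.

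In SAP 7.8.8 and 7.8.10, change the reference from 7.7.2 to 7.8.2 so that both use the same rule. This aligns the opening of the bleeding window with the protocol; it does not settle when the window closes.

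The cost is SAP text only. The protocol gives no competing TEAE definition, and no new data are needed. One downside is that a Day 1 event with a wrongly recorded time could be excluded; keeping untimed events as the default limits this. The other is that, if the eCRF collects no AE times, the change reaches only findings traceable to the pre-dose visit.

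### The only rule in SAP 7.8.2 for a recurring preferred term is maximum severity; applied as written to the by-relationship table, it can understate the number of subjects with a related event

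*SAP*

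**What the plan says.** SAP 7.8.2 lists eight summaries of treatment-emergent AEs. Among them are "All TEAEs by relationship to study drug" and, separately, "TEAEs potentially related to study drug", the latter also split by severity. The list opens with "Subject counts and percentages and event counts will be presented for the following TEAE summaries".

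Two counting rules follow the list. The first is "A subject will only be counted once per SOC and once per PT". The second is "If a subject reports more than one AE with the same PT, the AE with the maximum severity will be presented". Neither is tied to particular tables. Protocol 8.6 (Adverse Events) has the same pair of rules, placed before its list of summaries.

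The SAP then defines the categories: "An AEs relationship to study drug is assessed as related, possibly related, or not related". It does not say which category a subject takes when episodes of one PT were judged differently. It does have a conservative rule for gaps: "AEs with missing causality are assumed" to be related, and an AE with missing severity is counted at the highest severity possible. On listings it says: "Listings will be presented by subject for TEAEs, AESIs, serious AEs (SAEs), AEs leading to discontinuation of study drug, and AEs resulting in death".

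**The concern.** Maximum severity is the natural rule for a severity table, because it shows the worst grade each subject reached. It is the wrong rule for a relationship table, where the question is whether the subject had any event attributed to study drug. If severity picks the episode, the relationship shown is simply the one attached to the worst episode. A milder related episode then drops out of the subject count.

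The tables are descriptive, with no comparison between groups, so the tabulated counts and percentages are the result. Subjects receive three doses and are followed to Day 170, so a PT can recur in one subject. With 12 MAA868 subjects per cohort, moving one subject between rows is visible.

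The rule also works against the SAP's own caution. A mild event with missing causality is set to related, but a moderate unrelated recurrence of the same PT would override it in the subject count.

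**Working it through.** The documents give no figure for this point, so there is nothing to reproduce. The check applies the written rule to a constructed case.

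**Inputs**
- Selection rule: maximum severity per recurring PT (SAP 7.8.2; Protocol 8.6).
- Counting rule: each subject once per PT and once per system organ class (SOC) (SAP 7.8.2).
- Relationship categories: related, possibly related, not related (SAP 7.8.2).
- Arm size: 12 MAA868 and 4 placebo subjects per cohort (Protocol 5.3).

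**Constructed case.** One subject, one PT, two episodes: A is moderate and not related; B is mild and related.

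| Display | Maximum severity, as written | Strongest relationship |
|---|---|---|
| By relationship, subject count | not related 1, related 0 | not related 0, related 1 |
| By relationship, event count (if all events are counted) | not related 1, related 1 | not related 1, related 1 |

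Only the subject count and its percentage change.

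**Direction.** Order the categories as not related < possibly related < related. The category of the most severe episode can equal the highest category among all episodes but cannot exceed it. Any error is therefore towards less relatedness.

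**Potentially-related table, same case.** If related and possibly related events are selected first, episode B remains and the subject counts 1. If maximum severity is applied first, episode A is kept, then removed as unrelated, and the subject counts 0. The SAP does not state the order.

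**Size.** One subject in a 12-subject MAA868 arm is 1/12 = 8.3 percentage points for that PT. SAP Table 1 shows a single Placebo group. Pooled over two cohorts that is 2 × 4 = 8 subjects, and one subject is 1/8 = 12.5 points. Over three cohorts it is 3 × 4 = 12 subjects, and one subject is again 8.3 points.

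**Two cases without a rule.**
- Equal severity: if two episodes of a PT have the same severity but different relationship, there is no tie-break.
- SOC level: the selection rule covers only recurrences of the same PT. A subject with a mild related PT and a moderate unrelated PT in the same SOC is counted once for that SOC, with nothing to fix the severity or relationship row.

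**The case against.** The strongest reply is that the severity rule may have been meant only for the severity tables. Neither document says outright that it sets the row in the by-relationship table; that follows from its unrestricted wording. The SAP also refers to table shells, which are not part of the documents and might settle the matter. This limits how firmly intent can be stated. It does not remove the problem: no other rule for a recurring PT is written, so a programmer following the text has only maximum severity to apply.

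Several stronger readings are tempting, and the documents do not support them:

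- *Related events are hidden.* Every listed summary carries event counts, all TEAEs are listed by subject, and there are separate potentially-related tables. The event remains visible; the subject count is what suffers.
- *Two tables in the report will contradict each other.* That holds only if the potentially-related table selects related events first, and the SAP gives no order.
- *It happens whenever a worse or equal unrelated episode exists.* The rule produces this result only when the unrelated episode is strictly more severe.
- *One placebo subject is worth 25 points (1/4).* That needs a separate placebo column per cohort, and SAP Table 1 has one Placebo group.
- *Bleeding and injection-site signals depend on this table.* Injection-site reactions are tabulated by severity and duration (SAP 7.8.7). Bleeding is tabulated by adjudicated class (SAP 7.8.8). Neither uses investigator causality.

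It is also fair to say that the effect needs a particular coincidence within one subject. The protocol's endpoint (Section 2.2) is the occurrence of AEs and SAEs, not relatedness. These points keep the matter modest; they do not make the rule right for the table.

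**Conclusion.** The point stands in limited form. Maximum severity is the only stated rule for a recurring PT and is not confined to the severity tables. Followed literally, it places a subject with a related episode under *not related* when a strictly more severe unrelated episode of the same PT coexists. The error is confined to subject counts and percentages by relationship, and can only understate relatedness. It is 8.3 points per affected subject and PT in a 12-subject MAA868 arm.

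This assumes that the rule is applied as worded and that nothing in the table shells overrides it. The number of affected subjects cannot be derived from the documents and may be zero. The text should be corrected, but it is no ground for doubting the safety reporting as a whole.

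**What to change.** Amend SAP 7.8.2 as follows:

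1. Limit the maximum-severity rule to the severity tables, and apply it per PT and per SOC.
2. For the by-relationship table, count each subject once per PT and once per SOC at the strongest relationship: related, then possibly related, then not related, with missing causality counted as related.
3. For the potentially-related tables, select related and possibly related events first, then apply maximum severity where the table is split by severity.

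This also closes the SOC gap and removes the need for an equal-severity tie-break in the relationship table. Because Protocol 8.6 carries the same wording, the change should be noted in SAP Section 8, which now reports no departures from the protocol. The cost is a few sentences and a standard programming change; no new data are needed.
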